7. RESEARCH QUESTION AND OBJECTIVES

Research Question

What is the effectiveness of the EMA-authorized COVID-19 vaccines Comirnaty and Spikevax against severe COVID-19 and post-acute outcomes of SARS-CoV-2 infection?

Objective(s)

To generate additional evidence on the effectiveness of COVID-19 vaccines at preventing severe COVID-19 and post-acute outcomes of SARS-CoV-2 infection.

Specifically, this study has 6 objectives:

1. To assess the effectiveness of COVID-19 vaccination for the prevention of severe COVID-19 related outcomes (COVID-19 related hospitalisation or COVID-19 related death)
2. To assess waning of the effectiveness of COVID-19 vaccination for the prevention of severe COVID-19 related outcomes (COVID-19 related hospitalisation or COVID-19 related death)
3. To assess the effectiveness of COVID-19 vaccination for the prevention of all-cause mortality in the 3- and 6-months following discharge for COVID-19 related hospitalisation
4. To assess the effectiveness of COVID-19 vaccination for the prevention of new-onset type 1 Diabetes Mellitus in the 12 months after a SARS-CoV-2 infection
5. To assess the effectiveness of COVID-19 vaccination for the prevention of new-onset type 2 Diabetes Mellitus in the 12 months after a SARS-CoV-2 infection
6. To assess the effectiveness of COVID-19 vaccination for the prevention of cardiovascular events in the 12 months after a SARS-CoV-2 infection

	Phase II C3-002 – Study Protocol	
	Author(s): [name], [name], [name]	Version: v2.1
	Dissemination level: Public	

Table 7.1: Primary and secondary research questions and objective

A. Primary research question: Objectives 1-2

Objective:	To assess the effectiveness and waning of effectiveness of COVID-19 vaccination for the prevention of severe COVID-19 related outcomes
Hypothesis:	NA
Population (mention key inclusion-exclusion criteria):	All subjects aged 12 years and older, with at least 365 days of data availability in the respective database before index date (ID) with 
 • a 3rd-vaccine dose (1st booster dose) of Comirnaty or Spikevax. • at least 365days of data availability in the respective database • at least 90days of time elapsed since the last vaccine dose (i.e. the 3rd vaccine dose or 1st booster) at the time of study inclusion • at least 90days of time elapsed since the last record of a clinical diagnosis of COVID-19 or positive SARS-COV-2 test at the time of study inclusion.

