8.6.2. Outcomes

Primary outcomes of interest:

1. COVID-19 related hospitalisation
2. COVID-19 related death
3. All-cause mortality in the 3 months after discharge from a COVID-19 hospitalisation
4. All-cause mortality in the 6 months after discharge from a COVID-19 hospitalisation
5. Incidence of new-onset type 1 Diabetes Mellitus beyond the first 30d after SARS-CoV-2 infection
6. Incidence of new-onset type 2 Diabetes Mellitus beyond the first 30d after SARS-CoV-2 infection
7. Incidence of cardiovascular events (cerebrovascular disorders, dysrhythmias, ischemic and non-ischemic heart disease, pericarditis, myocarditis, heart failure and thromboembolic disease) in the 12 months after a SARS-CoV-2 infection.

Preliminary code lists are available in the appendix of this protocol for all outcomes.

SARS-CoV-2 infection and COVID-19

Positive test result for SARS-CoV-2

RT-PCR tests have high sensitivity and specificity for SARS-CoV-2. However, as a result of changes in the availability of population wide RT-PCR and home self-reported lateral flow tests during the Omicron period, it may not be possible to exclusively use RT-PCR tests when identifying positive test results in all datasets. All positive test results for SARS-CoV-2 observable in the database will therefore be included for the primary analysis, with documentation of what type of test it was to allow sensitivity analysis restricted to RT-PCR diagnosed patients as needed.

Clinical diagnosis of COVID-19

Whilst testing for SARS-CoV-2 was commonly performed in some of the countries that will be represented in this study, clinical diagnoses of COVID-19 were also made for many individuals. Diagnostic codes compatible with COVID-19 will therefore also be identified, with the recorded date being used in the analyses.

Hospitalization with COVID-19

Patients hospitalized with COVID-19 will be identified based on having a hospitalization along with a confirmatory diagnosis or test result of COVID-19 (both as defined above) within a time window from 21 days prior to admission up to three days following their admission. This time window has been chosen in accordance with previous studies commissioned by the EMA, and aimed to include those who had the diagnosis made prior to their hospitalization and to allow for a delay in test results or diagnoses to be made or recorded, while excluding individuals with hospital-acquired COVID-19.

COVID-19 related death

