Arterial thromboembolic events: will be identified by an acute myocardial infarction or acute ischemic stroke.

Cerebrovascular disorders will be identified by acute ischemic stroke, haemorrhagic stroke or transient ischemic attack.

Heart failure, cardiac arrhythmia, angina pectoris, pericarditis and myocarditis will be measured as outcomes.

Phenotypes for these outcomes have been developed and used in previous vaccine safety studies^{13,13}. Code lists are available in the appendix of this protocol.

	Phase II C3-002 – Study Protocol	
	Author(s): [name], [name], [name]	Version: v2
	Dissemination level: Public	

Table 8.6.2.1 Operational Definitions of Outcome

Outcome name	Details	Primary outcome ?	Type of outcome	Washout window	Care Settings ¹	Code Type	Diagnosis Position ²	Applied to study:	Measurement characteristics/ validation	Source of algorithm
Hospitalization with COVID-19	COVID-19 clinical diagnosis or SARS-CoV-2 positive test within a time window from 21 days prior to admission to 3 days after hospital admission	Yes	Binary, time-to-event	n/a	IP, OP	SNOMED	any	Cohort 1-4	n/a	n/a
COVID-19 related death	COVID-19 clinical diagnosis or SARS-CoV-2 positive test up to 28days prior to date of death	Yes	Binary, time-to-event	n/a	OP		n/a	Cohort 1-4	n/a	n/a
All-cause mortality	date of death	Yes	Binary, time-to-event	n/a	OP		n/a	Cohort 5-8	n/a	n/a
New-onset type 1 Diabetes Mellitus	New onset Type 1 Diabetes Mellitus within 30-365days following SARS-CoV-2 positive test or COVID-19 diagnosis	Yes	Binary, time-to-event	Anytime prior ID	OP		n/a	Cohort 5-8	n/a	n/a
New-onset type 2 Diabetes Mellitus	New onset Type 2 Diabetes Mellitus within 30-365days following SARS-CoV-2 positive test or COVID-19 diagnosis	Yes	Binary, time-to-event	Anytime prior ID	OP		n/a	Cohort 5-8	n/a	n/a
Cardiovascular events	New Cardiovascular event/complication recorded within 30-365days following SARS-CoV-2 positive test or COVID-19 diagnosis	Yes	Binary, time-to-event	365days prior to index date	OP		n/a	Cohort 5-8	n/a	¹³

OP = outpatient, n/a = not applicable

This document represents the views of the DARWIN EU® Coordination Centre only and cannot be interpreted as reflecting those of the European Medicines Agency or the European Medicines Regulatory Network.

	Phase II C3-002 – Study Protocol	
	Author(s): [name], [name], [name]	Version: v2
		Dissemination level: Public

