8.8.6 Stratified analyses, subgroup analyses and sensitivity analyses

All analyses will be stratified separately by vaccine brand (Comirnaty and Spikevax), and age at index date (i.e. age <65 years, ≥65 years).

Subgroup analyses will be conducted among people with immunocompromised status, recorded within 365 days prior to index date.

No sensitivity analyses are planned (Table 8.8.6.1).

Table 8.8.6.1 Sensitivity analyses – rationale, strengths and limitations

	What is being varied? How?	Why? (What do you expect to learn?)	Strengths of the sensitivity analysis compared to the primary	Limitations of the sensitivity analysis compared to the primary

	Phase II C3-002 – Study Protocol	
	Author(s): [name], [name], [name]	Version: v2.1
		Dissemination level: Public

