
11. LIMITATIONS OF THE RESEARCH METHODS

General limitations:

- The study will be informed by routinely collected health care data and so data quality issues must be considered.
- We will use large-scale propensity scores to minimize measured confounding, and NCOs to assess potential residual confounding. However, given the observational nature of our data, we cannot rule out remaining confounding, which could partially account for findings in this study.

Study-specific limitations:

- Mandatory PCR test for people who tested positive in lateral flow home tests were skipped in early 2022. As not all positive home tests were reported and recorded as clinical diagnoses in primary care databases, it is likely that non-severe SARS-CoV-2 infections are underreported after 02/2022. Moreover, underreporting of COVID-19 for asymptomatic case is to be expected. Underreporting of COVID-19 could lead to misclassification of outcomes for Objectives 4-6, namely post-acute COVID-19 complications (diabetes, cardiac events). For objectives 4-6, we require a minimum follow-up time of 12months after SARS-CoV-2 to identify cases of new-onset diabetes and/or cardiovascular complications. With this, only infections recorded before 02/2022 will be included in the study.
- Routine screening has been impacted by the pandemic, and therefore diagnoses of new conditions, e.g. T2DM might have been delayed depending on testing practices.
- COVID-19 related hospitalization is unlikely to be underreported as people are likely to be asked about previous SARS-CoV-2 infections at hospital admission (Objective 3). However, positive COVID-19 test results that occur around hospitalization do not constitute a hospitalization *due to* COVID-19.

	Phase II C3-002 – Study Protocol	
	Author(s): [name], [name], [name]	Version: v2.1
		Dissemination level: Public

We will use the data cuts currently onboarded for DARWIN EU for CPRD, IPCI and SIDIAP. However, none of those is currently covering the period of XBB variant predominance. We therefore designed the study to assess objectives 1 and 2 to start at the time the 4th vaccine doses were made available for people.

MANAGEMENT AND REPORTING OF ADVERSE EVENTS/ADVERSE REACTIONS

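### Hospitalisation outcome 1, presented as severe COVID-19, counts admissions for any reason near a COVID-19 record, and no planned analysis separates coincidental ones

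*Protocol*

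**What the plan says.** Objectives 1 and 2 (section 7) concern severe COVID-19, measured by COVID-19 related hospitalisation or death. Section 8.6.2 identifies the hospitalisation outcome by "having a hospitalization along with a confirmatory diagnosis or test result of COVID-19 (both as defined above) within a time window" that runs "from 21 days prior to admission up to three days following their admission". Table 8.6.2.1 repeats the rule as "COVID-19 clinical diagnosis or SARS-CoV-2 positive test within a time window from 21 days prior to admission to 3 days after hospital admission". It marks the outcome as primary, lists inpatient and outpatient care settings, gives the diagnosis position as any, and enters n/a for validation.

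Section 8.6.2 gives four grounds for the window: consistency with earlier EMA-commissioned studies, capturing diagnoses made before admission, allowing for delayed results or recording, and doing so "while excluding individuals with hospital-acquired COVID-19".

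Section 11, in a bullet tagged Objective 3, states that "positive COVID-19 test results that occur around hospitalization do not constitute a hospitalization" due to COVID-19. It gives neither direction nor size of bias. Section 8.8.6 says "No sensitivity analyses are planned (Table 8.8.6.1"), and that table is blank.

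**The concern.** The rule has no condition on reason for admission, an inpatient COVID-19 diagnosis, planned status or severity. A mild infection followed 18 days later by a delivery, a fracture or planned surgery qualifies. So does an elective admission with a positive screening test. None of the stated grounds for the window separates admission for COVID-19 from admission with COVID-19. Even the aim of excluding hospital-acquired infection is met only in part. Unless stays are linked, an infection caught on a ward can qualify through a readmission within 21 days.

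A coincidental admission depends on the vaccine only through infection. If protection against infection is weaker than protection against severe disease, counting these events lowers the reported VE. A reader could then not tell weak protection against severe disease from dilution by incidental admissions.

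**Working it through.** **Plan's own figure.** There is none to reproduce. The protocol states no event count, power or sample size (section 8.7 includes all eligible people).

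**Inputs from the protocol**
- Window: 21 days before to 3 days after admission, so 21 + 3 + 1 = 25 calendar days (section 8.6.2).
- Effect measure: VE = 1 - HR (Table 7.1, section 8.8.3).
- Illustrative anchor: 67.8% VE against hospitalisation, cited in section 6 as background and not as a design assumption.

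**Assumed inputs (not in the protocol)**
- Background all-cause admission rate: 5%, 10% or 20% per year.
- Risk of an admission caused by COVID-19 per recorded infection: 1%, 2% or 5%.
- VE against recorded infection: 10% or 20%.
- True VE against severe disease: 60%, as an alternative to the anchor.

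**Step 1: coincidental admissions per recorded infection**

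p = rate x 25/365.25, giving 0.34%, 0.68% and 1.37% at 5%, 10% and 20% per year.

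**Step 2: coincidental share of comparator-arm events**

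f = p / (p + causal risk)

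| Background per year | Causal risk 1% | 2% | 5% |
|---|---|---|---|
| 5% | 25% | 15% | 6% |
| 10% | 41% | 25% | 12% |
| 20% | 58% | 41% | 21% |

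**Step 3: observed VE**

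HR_obs = (1 - f) x HR_severe + f x HR_infection, so VE_obs = VE_severe - f x (VE_severe - VE_infection).

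With true VE 60%:
- f = 25%: 60 - 0.25 x 50 = 47.5% (VE against infection 10%); 60 - 0.25 x 40 = 50% (20%).
- f = 12%: 60 - 0.12 x 50 = 54%; 60 - 0.12 x 40 = 55.2%.

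With the 67.8% anchor and VE against infection of 20%, VE_obs is 63.0%, 58.2% and 53.5% at f = 10%, 20% and 30%.

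**Boundary check.** If VE against infection equals VE against severe disease, the shift is zero at every f.

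**What the model leaves out.** Step 1 counts admissions per recorded infection. Infections detected only because a patient was screened at admission are not represented, and they would raise f.

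**The case against.** The trade-off is disclosed, has a stated rationale, and follows earlier practice. Section 8.6.2 itself heads the outcome as hospitalisation with COVID-19. That stands: this is an acknowledged limitation left without a check, not an oversight. It is also a reason to leave the primary definition alone.

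Every input to the size is assumed. Section 11 expects non-severe infections to be under-recorded after 02/2022. That would raise the admission risk per recorded infection and lower the coincidental share. At 10% background, moving the causal risk from 2% to 5% cuts the share from 25% to 12%. This stands too, with admission screening working the other way, so no single figure should be quoted.

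Other planned features do not fill the gap. The possible RT-PCR restriction in section 8.6.2 concerns test type. Negative control outcomes (section 8.8.3) are planned to detect residual confounding, not to remove coincidental events. The absence of a sensitivity analysis cannot be read as deferral to an analysis plan, because section 8.8.6 states it outright.

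Three stronger readings are tempting but not supported:
- **The waning curve is distorted.** An argument that the coincidental share rises as disease becomes milder concerns calendar time. Objective 2 runs by time since an index date shared within each pair, and no distortion on that scale has been shown.
- **Objective 3 is diluted in the same way.** Its outcome also requires death within 3 or 6 months of discharge. The arithmetic above covers hospitalisation alone.
- **Coincidental events could reach about 80%.** That pairs 30% background admission with 0.5% causal risk. Both would be expected to rise with age, so the pairing is an implausible corner.

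Feasibility of a stricter outcome is also open. Table 8.2.1 lists hospital linkage for SIDIAP, but the SIDIAP description in section 8.2 says specialist-setting diagnoses are not included.

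**Conclusion.** The point holds as a non-specific primary outcome whose non-specificity the protocol concedes but does not examine. The definitional part needs no assumption. The direction (VE pulled toward VE against infection) needs two: VE against recorded infection is below VE against severe disease, and among matched infected people coincidental admission does not depend on dose. The size cannot be settled from the documents. Under the assumed ranges the coincidental share is about 6-58%. In the middle of that range (12-25%), a true VE of 60% would read about 47-55%. This warrants a change to the plan but does not invalidate the primary analysis.

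**What to change.** Keep the primary definition, for comparability with the earlier studies it follows. Make these additions:

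1. In section 8.8.6 and Table 8.6.2.1, pre-specify one sensitivity outcome, reported beside the main one: admissions with a COVID-19 condition code recorded during that inpatient stay, excluding stays coded for delivery, injury or a planned procedure.
2. Apply it in each database where inpatient diagnoses are confirmed to be available. Tables 8.2.1 and 8.6.2.1 point to SIDIAP; reconcile this with the SIDIAP description in section 8.2. The abstract's outcome list says hospitalisation is not available in IPCI, while section 8.8.3 assesses it there, so settle that as well.
3. If inpatient codes are not available, use a narrower window around admission as the fallback.
4. Link transfers and immediate readmissions into one stay, so that a ward-acquired infection cannot qualify through a later admission date.
5. Reconcile the SIDIAP data lock (06/2022, Table 8.2.1) with the 01/08/2022 start of the fourth-dose period in the abstract and the country-specific roll-out start in section 8.3. On the first two dates, SIDIAP adds no events to Objectives 1-2, under either outcome definition.

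The cost is one more outcome definition in the study package. The stricter outcome will have fewer events and may be feasible in only one database.

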8.7 Study size

For each database, all individuals that satisfy the eligibility criteria for a study cohort will be included.

8.8 Analysis

All analyses will be conducted separately for each database, and will be carried out in a federated manner, allowing analyses to be run locally without sharing patient-level data.

Before sharing the study package, test runs of the analytics will be performed on a subset of the data sources and quality control checks will be performed. After all the tests are passed (see section 11 Quality Control), the final package will be released in a version-controlled study repository for execution against all the participating data sources.

The data partners will locally execute the analytics against the OMOP-CDM in R Studio and review and approve the by default aggregated results. They will then be made available to the Principal Investigators and study team in the Digital Research Environment. All results were locked and timestamped for reproducibility and transparency.

8.8.1 Patient privacy protection

Cell counts <5 will be suppressed to comply with the database's privacy protection regulations.

8.8.2 Descriptive statistics

For each analyses, summary descriptive analyses will be conducted including age, sex, key variables for matching and selected comorbidities where relevant.

8.8.3 Objectives 1-2: Vaccine effectiveness to prevent severe infection

Objectives 1 and 2 will assess the effectiveness of a 4th COVID-19 vaccine dose in people with 3 vaccine doses.

Study population

All people with a 3rd vaccine dose of Comirnaty or Spikevax will be included from the source population. Cohorts will be generated separately for Comirnaty and Spikevax, respectively.

Study inclusion: Sequential matching

Inclusion will be conducted using a sequential matching design, with similar designs being used in previous studies assessing vaccine effectiveness. Previous research showed matching to adequately reduce measured confounding in vaccine effectiveness research when including key variables such as geographic location²⁴.

Matching process using key confounders and Propensity Scores

For each calendar week starting from the day when a 4th vaccine dose (i.e. 2nd booster vaccine) became available/recommended in the respective country, people will be assigned to two cohorts: people who received a 4th vaccine dose during that week and people who did not receive a 4th dose.

Using the first day of the respective week as “preliminary” index date for non-boostered people, and the date of the 4th dose for booster-vaccinated people, the following inclusion criteria will be applied:

	Phase II C3-002 – Study Protocol	
	Author(s): [name], [name], [name]	Version: v2.1
		Dissemination level: Public

- At least 365 days of data availability in the respective database
- At least 90days of time elapsed since the previous vaccine dose (i.e. the 3rd or 4th vaccine dose)
- At least 90days of time elapsed since the last record of a clinical diagnosis of COVID-19 or positive SARS-COV-2 test.

Among those people in the cohorts who received or not received a 4th dose and met the inclusion criteria, non-boostered people will be matched 1:1 to a person receiving their 4th dose, based on key confounders and large-scale propensity scores using nearest neighbor matching, with caliper width 0.2 standard deviation. Key confounders will comprise but are not limited to:

- Age (e.g. 5-year age bands)
- Sex (exact)
- Geographic location (exact)
- Previous vaccine brands (e.g. homologous or heterologous vaccination scheme)
- Time from previous vaccination
- History of conditions for prioritization for vaccination
- immunocompromised status
- previous SARS-CoV-2 diagnosis (>90days before index date)

Large-scale propensity scores (PS) will be computed to estimate the probability of receiving a 4th vaccine dose. Covariates to be included in the large-scale PS will be selected from co-medications and comorbidities recorded prior to cohort-specific index dates. Among those, covariates with a prevalence below 0.5% in the study population will be omitted. Logistic regression with LASSO regularization will then be used for variable selection. The list of selected covariates will be manually screened by 2 epidemiologists/clinical domain experts to exclude potential instrumental variables.

The same procedure will be conducted in the calendar week after, with previously non-boostered people being allowed to be included in the booster cohort once they change exposure status. Non-boostered people can only be matched once to a booster counterpart during the whole study. With matching, non-boostered counterparts will be assigned the date of when the booster counterpart received their 4th vaccine dose as their “final” index date (index date for the matched pair).

All booster and matched non-boostered people from sequential weekly matching will be combined into the booster and non-boostered cohort for subsequent analyses. The study inclusion and sequential matching process is illustrated in [Figure 8.8.3.1](#) below.

[figure not shown]

	Phase II C3-002 – Study Protocol	
	Author(s): [name], [name], [name]	Version: v2.1
	Dissemination level: Public	

Figure 8.8.3.1 Study inclusion and sequential matching process

	Phase II C3-002 – Study Protocol	
	Author(s): [name], [name], [name]	Version: v2.1
		Dissemination level: Public

Follow-up

In the matched cohorts, people will be followed up from their index date until the earliest of

- End of their observation (i.e. date of data extraction, death)
- 2nd booster vaccination for unvaccinated group, 3rd booster for vaccinated group etc.
- COVID-19 related hospitalization or death, with outcome date being defined as the date of first COVID-19 diagnosis/positive test related to hospitalization or death.

Follow-up will be censored for the matched pair if one counterpart is censored, but not if one counterpart experiences the outcome.

Outcomes

The outcomes are defined in detail in section 8.6.2.

COVID-19 related hospitalization will be assessed for SIDIAP and IPCI. COVID-19 related death will be assessed for CPRD, IPCI and SIDIAP.

Statistical Analyses

Objective 1: Vaccine effectiveness

Cox proportions hazard models will be used to calculate hazard ratios (HR) for the outcomes of COVID-19 related hospitalisation and COVID-19 related death.

Negative control outcomes will be used as an additional measure to measure any potential residual confounding. NCO are outcomes not causally associated with the exposure of interest²⁶, here COVID-19 vaccination. However, their association with vaccination is ideally impacted by the same type of unmeasured confounding, e.g. healthcare-seeking behavior, as the vaccination-outcome association²⁷. In the scenario of potential unmeasured confounding being detected by NCO, empirical calibration²⁵ for HR might be considered to minimise bias.

Vaccine effectiveness will be calculated as $1 - HR$. Kaplan Meier plots and/or cumulative incidence plots will be used to illustrate survival analyses.

The proportional hazard assumption will be tested visual investigation of log(-log) plots. In the scenario of substantial violation of the proportional hazard assumptions, alternative models/model adaptations will be used.

Objective 2: Waning of vaccine effectiveness

Hazard ratios will be calculated for subsequent time windows after index date, i.e. in bi-weekly intervals. Monthly intervals will be used in case of small event counts to increase sample size and power if needed. Vaccine effectiveness will be calculated as $1 - HR$.

Kaplan Meier plots and/or cumulative incidence plots will be used to illustrate survival analyses.

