8.8.4 Objective 3: Vaccine effectiveness to prevent COVID-19 related mortality

Objective 3 will assess vaccine effectiveness to prevent all-cause mortality in the 3 months/6 months after discharge from a COVID-19 hospitalisation. This objective will be assessed for SIDIAP and IPCI only, as no information on hospitalisation are available in CPRD.

	Phase II C3-002 – Study Protocol	
	Author(s): [name], [name], [name]	Version: v2.1
		Dissemination level: Public

The following comparisons will be conducted:

- 1st dose vaccinated vs. 2nd dose vaccinated [cohort 5 vs. 6]
- 2nd vaccinated vs. 3rd dose vaccinated [cohort 6 vs. 7]
- 3rd dose vaccinated vs. 4th dose vaccinated [cohort 7 vs. 8]

Study population

The study populations will be derived similar to the inclusion process outlined for objectives 1-2 above, including sequential matching. The following inclusion criteria will be applied:

- At least 365 days of data availability in the respective database
- At least 90days of time elapsed since the previous vaccine dose for the 3rd or 4th vaccine dose
- At least 21days of time elapsed since the previous vaccine dose for the 2nd vaccine dose
- At least 90days of time elapsed since the last record of a clinical diagnosis of COVID-19 or positive SARS-COV-2 test.

Outcomes

For contextualization, we will assess vaccine effectiveness to prevent COVID-19 hospitalization for the mentioned comparisons. The primary study outcome will be COVID-19 hospitalization followed by death within 3 or 6 months from discharge.

Statistical Analyses

Vaccine effectiveness analyses for COVID-19 related mortality following hospital discharge:

Incidence rates will be calculated for the matched cohorts and both outcomes. Cox proportional hazard models will be calculated for each outcome to provide HR. Follow-up will start at index date, i.e. the date of vaccination with respective new dose for matched pairs.

Negative control outcomes will be used as an additional measure to measure potential residual confounding. In the scenario of potential unmeasured confounding being detected by NCO, empirical calibration²⁵ for HR might be considered to minimise bias.

Kaplan Meier plots and/or cumulative incidence plots will be used to illustrate survival analyses.

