8.8.5 Objectives 4-6: Vaccine effectiveness to prevent post-acute COVID-19 complications

Objectives 4-6 evaluate vaccine effectiveness to prevent post-acute COVID-19 complications, namely new onset diabetes and cardiovascular complications, and will be conducted in all 3 databases.

Similar to objective 3, we will compare people with 1st dose vaccination vs. 2nd dose vaccination [cohort 5 vs. 6], 2nd dose vaccination vs. 3rd dose vaccination [cohort 6 vs. 7] and 3rd dose vaccination vs. 4th dose vaccination [cohort 7 vs. 8].

Study population

The study populations will be derived similar to the inclusion process outlined for objectives 1-3 above, including sequential matching. Inclusion criteria will be applied as outline in section 8.8.4 for Objective 3.

For objectives 4 and 5, people with the respective outcomes of interest, i.e. diabetes recorded anytime before their index date will be excluded for the respective objective. For objective 6, an outcome-free washout window of 365days prior to index date will be implemented.

	Phase II C3-002 – Study Protocol	
	Author(s): [name], [name], [name]	Version: v2.1
		Dissemination level: Public

We will require at least 12 months of follow-up after SARS-CoV-2 infection to assess post-acute complications for outcomes 5, 6, and 7. If people die within 12 months after COVID-19 they will contribute patient-time until death to the analyses. Only infections recorded 12 months before the end of data availability will be included.

Outcomes

- SARS-CoV-2 infection [for contextualization]
- SARS-CoV-2 infection + New onset diabetes Type 1 diabetes within 30-365 days after COVID-19
- SARS-CoV-2 infection + New onset diabetes Type 2 diabetes within 30-365 days after COVID-19
- SARS-CoV-2 infection + cardiovascular events (cerebrovascular disorders, dysrhythmias, ischemic and non-ischemic heart disease, pericarditis, myocarditis, heart failure and thromboembolic disease) in the 12 months after a SARS-CoV-2 infection

Vaccine effectiveness analyses for post-acute COVID-19 complications:

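### Comparators are chosen by whole-week dosing status while follow-up starts inside that week, so they are selected on staying undosed for up to 6 days after time zero

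*Protocol*

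**What the plan says.** Section 8.8.3 (Objectives 1-2) builds the cohorts week by week. People are sorted into "people who received a 4th vaccine dose during that week and people who did not receive a 4th dose". Not receiving the dose refers to that week rather than for good, because the process repeats in the next week with "previously non-boostered people being allowed to be included in the booster cohort once they change exposure status". The abstract describes the same procedure.

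Three dates are then in play:

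- **Eligibility:** checked on the first day of the week as a preliminary "index date for non-boostered people, and the date of the 4th dose for booster-vaccinated people".
- **Time zero:** after 1:1 matching, "non-boostered counterparts will be assigned the date of when the booster counterpart received their 4th vaccine dose" as their final index date.
- **Follow-up:** for Objective 3, section 8.8.4 says "Follow-up will start at index date, i.e. the date of vaccination with respective new dose for matched pairs", with no lag. Section 8.8.5 says the same for Objectives 4-6.

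The procedure carries over to 1 versus 2, 2 versus 3 and 3 versus 4 doses. Section 8.8.5 states: "The study populations will be derived similar to the inclusion process outlined for objectives 1-3 above, including sequential matching". Section 8.8.4 makes the same kind of reference for Objective 3. Section 8.8.6 plans no sensitivity analyses.

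**The concern.** The cohort split uses the whole week, but the pair's clock starts on a day within it. Take a person dosed on day 1. Someone dosed on day 5 was undosed and eligible on day 1, yet cannot be the comparator, because that person belongs to the week's dosed cohort. Someone who tests positive on day 3 and so misses the dose can be. Comparators are thus selected on what happens after time zero, for 6 days if indexed on day 1 and 0 days if indexed on day 7.

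If illness delays vaccination, this loads early events into the comparator arm and the new dose looks protective when it is not. The distortion ends with the index week, so in the bi-weekly windows of Objective 2 it would add a little apparent early effect that then fades. The negative control outcomes are presented in section 8.8.3 as a check on unmeasured confounding such as healthcare-seeking, so they are not aimed at this mechanism.

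**Working it through.** The protocol gives no uptake, power or bias figure, so there is none to reproduce. The check asks what hazard ratio the rule yields when the truth is 1.

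**Inputs from the protocol:** whole-week split, time zero on the counterpart's dose date, no lag, joint censoring of the pair at the next dose, and 1:1 matching (section 8.8.3; start of follow-up also in 8.8.4 and 8.8.5).

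**Assumptions, not in the protocol:** a share *p* of eligible people is dosed per week at a constant daily rate *v* = −ln(1 − *p*)/7; a person who is infected or admitted is not dosed in the rest of that week; comparators are infection-free at time zero; follow-up is capped at 180 days.

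**Step 1, comparator hazard.** Let *L* be the days left in the week at time zero. A well person stays undosed to the end of the week with probability exp(−*vL*). A person infected *t* days after time zero only has to be undosed up to *t*, with probability exp(−*vt*). Among retained comparators the infection hazard is therefore multiplied by exp(−*vt*)/exp(−*vL*) = exp(*v*(*L* − *t*)) for *t* < *L*, and by 1 afterwards.

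**Step 2, average over index days**, with density proportional to exp(−*vd*) for index day *d* and *L* = 7 − *d*:

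- A = mean of *L*, the follow-up inside the index week;
- B = mean of (exp(*vL*) − 1)/*v*, the same time weighted by the inflated hazard;
- C = mean of (1 − exp(−*v*(*T* − *L*)))/*v*, the follow-up after that week until the comparator's dose or *T* days.

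Null ratio = (A + C)/(B + C).

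| Weekly uptake | *v* | A | B | C, 14 days | Ratio, 14 days | C, 180 days | Ratio, all follow-up |
|---|---|---|---|---|---|---|---|
| 10% | 0.0151 | 3.56 | 3.69 | 9.63 | 0.990 | 61.77 | 0.998 |
| 30% | 0.0510 | 3.71 | 4.21 | 7.95 | 0.959 | 19.62 | 0.979 |
| 50% | 0.0990 | 3.90 | 5.05 | 6.31 | 0.899 | 10.10 | 0.924 |
| 80% | 0.2299 | 4.40 | 8.70 | 3.83 | 0.657 | 4.35 | 0.671 |

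For example, at 50% over all follow-up: (3.90 + 10.10)/(5.05 + 10.10) = 14.00/15.15 = 0.924. Counting whole days instead, with *L* = 6, 5, …, 0, the same formulas give slightly weaker ratios over all follow-up: 0.937 at 50% and 0.712 at 80%.

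**Step 3, simulation** (8 million people per scenario, infection risk 0.5% per week, illness deferring the dose by 28 days). Null hazard ratios over all follow-up:

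| Scenario | 10% | 30% | 50% | 80% |
|---|---|---|---|---|
| Plan's rule, full deferral | 1.000 | 0.978 | 0.923 | 0.669 |
| Plan's rule, half of ill people defer | – | – | 0.962 | 0.811 |
| Plan's rule, no deferral | – | – | 0.998 | 1.043 |
| Status taken on the index date, full deferral | 0.999 | 1.000 | 0.985 | 0.987 |

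Standard errors of the log hazard ratio are between 0.004 and 0.014. At an infection risk of 0.1% per week, the plan's rule gives 0.932 at 50% and 0.663 at 80%.

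**The case against.** **The wording may not be meant this way.** Section 8.5 says the counterpart has one dose fewer when matched, and ties the inclusion criteria to the matched counterpart's index date. That conflicts with the first-day check in 8.8.3, but it does not say that dose status is read on the index day, so the weekly split stands. For Objectives 3-6 the process is only described as similar to that of 8.8.3.

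**The direction needs an outside assumption.** This stands. Without deferral there is no false effectiveness.

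**The effect is negligible where the rule is written.** This stands for a slow 4th-dose campaign: at 10% weekly uptake, false effectiveness is about 0.2% over all follow-up and 1% in the first 14 days.

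**High uptake is speculative.** Also fair. With 1:1 matching and each undosed person used once, at most 20/80 = 25% of those dosed in a week could be paired at 80% uptake, so high-uptake groups yield few pairs. The minimum interval before a second dose is also inconsistent: 21 days in sections 8.4, 8.5 and 8.8.4, but 90 days in Table 7.1. Those passages must be reconciled, and how far matched people fall due together depends on the result.

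**The modelled endpoint is not primary for Objectives 3-6.** This stands and limits the claim. A reader might carry the large ratios over to post-discharge death, diabetes or cardiovascular events. Sections 8.8.4 and 8.8.5 report hospitalisation and infection only for context. The primary outcomes are composites whose event date is not fixed there; dating at first diagnosis or test is stated only for Objectives 1-2.

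**Conclusion.** The design flaw is in the text: comparators are selected on up to 6 days of non-vaccination after time zero. The bias is towards effectiveness if ill people postpone the dose.

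For infection or admission with full deferral, false effectiveness over all follow-up is about 0.2% at 10% weekly uptake, 2% at 30%, 8% at 50% and 33% at 80%. It does not threaten the 4th-dose estimates at slow uptake. It could matter for 1 versus 2 doses: matching on time since the previous dose, age and location brings together people who fall due together, and censoring at the next dose leaves little later follow-up to dilute the first week. How much it matters there cannot be fixed, because the protocol gives no uptake.

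Two stronger readings are not supported. One is that the rule creates large false effectiveness for the primary outcomes of Objectives 3-6. The other is that repairing it makes those analyses unbiased. Joint censoring at the next dose may itself be informative for the composites, which is a separate issue.

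**What to change.** In section 8.8.3, define the comparator as a person who has not received the next dose up to and including the pair's index date, whatever happens later that week. Apply all eligibility criteria, including the recent-infection exclusion, on that same date, and align section 8.5 and the abstract. If the comparator is dosed later in the same week, censor the pair on that date and let the person enter the dosed cohort. State this for all dose comparisons in 8.8.4 and 8.8.5.

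The cost is protocol wording and matching code, with no extra data. Some pairs will contribute only a few days of follow-up instead of never being formed. The change removes the selection on later non-vaccination; it does not deal with informative censoring at the next dose for the composite outcomes.
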